3.1 Objectives

Primary Objective:

To record the incidence and oncological outcome when a fertility preserving cancer treatment is applied in young women and compare the oncological outcome with a control group.

Secondary Objective(s):

To record the incidence and fertility outcome when a fertility preserving cancer treatment is applied in young women and compare the obstetrical and neonatal outcome with the general population.

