3.3 Sample size

We aim for at least 500 cases per tumour type + 1 control patient per study patients (resulting in 500 control patients per tumour type). This is a minimum that allows us to calculate the oncological prognosis (secondary objective).

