3.4 Study procedures

In women younger than 40 years old with a cancer diagnosis for whom a fertility preserving treatment is applied, the most important oncological data will be registered, as well as information on the fertility and oncological outcome. Control patients are women who are younger than 40 years of age diagnosed with cancer and who received standard treatment. All types of cancer and all types of treatment will be registered. Patients can be included both prospectively and retrospectively. For every study patient, we include one control patient.

Recruitment of patients:

Because information on pregnant state is not available in most cancer registries prospective recruitment of patients is done as followed networking (e.g. INCIP), newsletters, presentation at conferences for obstetricians, oncologists, haematologists, and also a website for professionals (www.cancerinpregnancy.org) and for patients (<http://www.uzleuven.be/kanker-en-zwangerschap>).

We will collect the following data:

At baseline:

Oncological data include type of cancer, the date of diagnosis, tumour histology, stage of the disease, the type of treatment, cancer recurrence and survival.

Fertility data include gravidity and parity, menstrual pattern after cancer treatment, conception (artificial or natural), obstetrical complications, gestational age at delivery and mode of delivery (induction, caesarean section, spontaneous labour).

Paediatric data that will be collected include birth weight, gender, congenital malformations, admission to neonatal care unit and reason of admission.

Annually until end of study:

We will request information from the treating physician regarding patient's health status (pregnant yes/no, relapse yes/no, site of relapse, treatment of relapse, date of relapse, date of death if applicable).

This study does not involve any direct input or effort from the patient. Only the collection of existing information through the medical records is aimed for.

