6. STATISTICAL ANALYSIS

We plan to use descriptive statistics (mean +/- standard deviation), two-sided tests, and Wilcoxon rank sum test to compare continuous variables in two groups, for more than two groups, the Kruskal-Wallis exact test will be used. For comparing a proportion with an expected value, a binominal exact test will be used. Results are considered significant at $P < .05$.

Analysis will be performed with SAS (version 9.2) and Statistical Package for Social Sciences for Windows (version 16). Statistical analysis will be performed under supervision of Prof. [name] (Leuven Cancer Institute, Belgium).

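### The only test that fits the general-population comparison of obstetric and neonatal outcomes takes one expected probability, so case mix alone can make it significant

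*Protocol*

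**What the plan says.** Protocol section 3.1 sets, as a secondary objective, to "compare the obstetrical and neonatal outcome with the general population". The control group is named there for the oncological outcome only, so the reference for births is external.

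Section 6 gives one method for a proportion against an external value: "For comparing a proportion with an expected value, a binominal exact test will be used". Tests are two-sided at P < .05. The section names no standardisation, stratification, regression or allowance for clustering.

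Section 3.4 lists gravidity and parity, menstrual pattern, "conception (artificial or natural), obstetrical complications, gestational age at delivery and mode of delivery", and for the child "birth weight, gender, congenital malformations, admission to neonatal care unit and reason of admission". Plurality is not in the list. Mode of conception and parity are collected, but section 6 gives them no role. Pregnancy status is requested every year, so more than one pregnancy per woman is foreseeable.

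Section 3.3 says "We aim for at least 500 cases per tumour type". That number counts women and is tied to oncological prognosis. The protocol gives no expected number of deliveries, no reference rate and no power for the obstetric comparison.

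**The concern.** A one-sample exact binomial test compares an observed count with one fixed probability and assumes independent units. This cohort differs from a general population by design. It is international, covers all cancers and treatments, is limited to women under 40, and is likely to include assisted conceptions, since section 2 describes embryo cryopreservation as the most used option. If the expected value comes from a population with another mix of country, age, parity or twins, the test can reject because of the mix alone.

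The study is meant to inform clinicians and patients about fertility-sparing treatment. An excess of preterm birth or neonatal admission that reflects more twins or more first births could be read as harm from that treatment. If plurality is not recorded, a later analysis plan cannot separate twins from singletons.

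**Working it through.** The plan gives no figure to reproduce. From the documents come the exact binomial test, the two-sided 5% level and the comparison with the general population. **Every rate and delivery count below is an assumption.**

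**1. Does the test hold its level when its assumptions hold?** With independent births at the reference rate (5%, 8% or 10%; 100, 200 or 500 births), the actual level is 3.3% to 4.9%. The test itself is sound, so any distortion comes from the reference value or the units.

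**2. Twin rate only, counted per delivery.** Assume preterm birth in 6% of singleton and 50% of twin deliveries, and a population twin rate of 1.5%.

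- Expected value: 0.985 × 0.06 + 0.015 × 0.50 = 0.0591 + 0.0075 = 6.66%.
- Cohort rate at twin rate t: (1 − t) × 0.06 + t × 0.50.
- Rejection probability: the binomial probabilities at the cohort rate, summed over all counts for which the exact two-sided P against 6.66% is below .05.

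| Cohort twin rate | Cohort preterm rate | 100 deliveries | 300 deliveries | 500 deliveries |
|---|---|---|---|---|
| 3% | 7.3% | 6.6% | 8.4% | 9.5% |
| 6% | 8.6% | 15.5% | 29.2% | 41.0% |
| 10% | 10.4% | 34.6% | 68.9% | 86.5% |

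The risk within singletons and within twins is the same in cohort and population throughout.

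**3. The same question per infant, with other assumptions.** Take a reference rate of 8%, twins as 3% of infants and a twin preterm risk of 55%. The singleton risk is then (0.08 − 0.03 × 0.55) / 0.97 = 6.55%. If twins are 10% of cohort infants, the crude rate is 0.90 × 0.0655 + 0.10 × 0.55 = 11.4%. The test rejects in 26%, 43% and 73% of studies at 100, 200 and 500 births (simulation, co-twins concordant). With twins as 6% of infants it rejects in 9%, 14% and 21%. With the twin share equal to the reference it rejects in about 5%.

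**4. Any case-mix difference.** If the cohort's baseline risk is a multiple of a 5-10% reference for reasons other than treatment:

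| Risk ratio from case mix | 100-200 births | 500 births |
|---|---|---|
| 1.2 | 8-17% | 15-31% |
| 1.5 | 22-61% | 63-93% |
| 2.0 | 55-98% | 99-100% |

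**5. Repeat pregnancies only, correct marginal rate.** Design effect 1 + (m − 1)ρ, with m the mean deliveries per woman and ρ the within-woman correlation; level 2 × [1 − Φ(1.96/√DE)].

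- m = 1.3, ρ = 0.2: DE = 1.06, level 5.7%.
- m = 2.0, ρ = 0.4: DE = 1.40, level 9.8%.

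A simulation of the exact test itself (reference 8%, 200-500 births, correlation 0.2-0.8) gives 5.0-5.8% with 10% of births in pairs and 5.9-9.6% with 50%. Clustering is the smaller problem.

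**The case against.** The strongest reply is that section 6 names no outcome, no reference source and no counting unit. A reader might infer that the protocol tests against a single crude population figure and counts twins and repeat pregnancies as independent. It says neither. An expected value can be standardised, one delivery per woman can be the unit, and such details often sit in an analysis plan. Even the link between the test and the births is an inference, though a reasonable one because no other external comparison is described. This part stands: the test is not invalid in itself.

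Second, the larger rejection rates need a twin rate of 10% and several hundred deliveries, and the documents support neither. The 500 in section 3.3 is women, not births. At a doubled twin rate, rejection is only 7-8% at 100 to 300 deliveries. This stands too, and is why ranges are shown. The calculations in steps 2 and 3 concern preterm birth; neonatal admission was not calculated separately.

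Third, extra twins after assisted conception may belong to the pathway from fertility preservation to birth outcome. A crude comparison answers the descriptive question in section 3.1, which makes no causal claim, and matching on plurality would remove part of what the study should describe. This also stands and shapes the fix.

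What the reply does not meet is that the stated inferential method has no means of handling case mix, and that the protocol's data list omits plurality. An analysis plan can repair the first, but not the second if the field was never collected.

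**Conclusion.** The concern holds in a limited form. On the most natural reading of sections 3.1 and 6, the general-population comparison rests on a test that cannot account for case mix. A significant excess could therefore arise with no direct effect of fertility-sparing treatment. Under the step 2 assumptions this happens in about 7-35% of tests at 100 deliveries and 8-69% at 300, for cohort twin rates of 3-10%. Clustering of repeat pregnancies adds little (a level of about 5-10%) and disappears with one delivery per woman.

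The documents do not support the stronger claim that the protocol fixes a crude reference or treats repeat pregnancies and twins as independent. Nor is the crude difference spurious as description: a cohort with more twins does have more preterm births. The error would lie in attributing that difference to the treatment. The objective is secondary and the study is not randomised, so this should be corrected but does not threaten the primary oncological comparison.

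**What to change.** - **Section 3.4:** add plurality, recorded per delivery.
- **Section 6, reference and unit:** say which outcomes are compared with the general population, where the expected values come from, and what the counting unit is.
- **Section 6, inference:** keep the crude comparison as description. Replace the binomial test as the basis for inference with an observed/expected ratio and 95% CI, with expected values standardised by country, maternal age and parity.
- **Dependence:** use the first post-treatment delivery per woman, or all deliveries with a cluster-robust variance by woman.
- **Presentation:** show singleton deliveries separately, and report natural and artificial conceptions separately. Do not rely on a plurality-adjusted result alone, because twinning after assisted conception may be part of the pathway. The main ratio will still carry any excess of twins, so it has to be read beside the singleton result.

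The cost is extra analysis work, national reference tables and one added field, which may be incomplete in retrospective records. Treatment and recruitment are unaffected.

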7. SAFETY REPORTING

7.1 Section 10 WMO event

In accordance to section 10, subsection 1, of the WMO, the investigator will inform the subjects and the reviewing accredited ethical committee if anything occurs, on the basis of which it appears that the disadvantages of participation may be significantly greater than was foreseen in the research proposal. The study will be suspended pending further review by the accredited METC, except in so far as suspension would jeopardise the subjects' health. The investigator will take care that all subjects are kept informed.

7.2 AEs, SAEs and SUSARs

Definitions in Law of May 7, 2004 concerning experiment on the human person

Adverse event (AE): any untoward medical occurrence in a patient or subject of the treated group during an experiment, and which does not necessarily have a causal relationship with this treatment

Serious adverse event (SAE): any untoward medical occurrence or effect that results in death, is life-threatening, requires hospitalisation or prolongation of existing hospitalisation, results in persistent or significant disability or incapacity, or is a congenital anomaly or birth defect;

Suspected unexpected serious adverse reaction (SUSAR): is an AR that is serious and unexpected (meaning that nature or severity of the AR is not consistent with the Investigational Medicinal Product reference safety information, which is the Investigator's Brochure) and is judged by either the investigator or the sponsor as having a reasonable suspected causal relationship with the investigational medicinal product.

7.2.1 Adverse events (AEs)

All adverse events caused by study interventions reported spontaneously by the subject or observed by the investigator or his staff will be recorded. We do not expect any study related adverse events for this study.

7.2.2 Serious adverse events (SAEs) expected

The investigator shall report all study intervention-related serious adverse events immediately, after first knowledge, to the sponsor except for those that the protocol or investigator's brochure identifies as not requiring immediate reporting. The immediate report shall be followed by detailed, written reports. The immediate and follow-up reports shall identify subjects by code numbers. For reported study intervention related deaths of a subject, the investigator shall supply the sponsor and the accredited ethics committee with any additional information requested.

The sponsor shall keep detailed records of all study intervention-related adverse events which are reported to him by the investigator or investigators. These records shall be submitted to the minister if the experiment is being conducted in Belgium, if he so requests. Regarding those study intervention-related serious adverse events the Principal Investigator will take all reasonable measures, in consultation with Sponsor, to protect subjects at risk following the occurrence of such events.

Participation in this study holds an extremely low risk of AEs and study intervention-related SAEs since no invasive interventions are performed. Since this study holds an extremely low risk of a study intervention-related SAE and no invasive interventions are performed, this present study is relieved of reporting non study related SAEs.

7.3 Data Safety Monitoring Board (DSMB)

Data safety monitoring board is not needed. As this study is a study with extremely low risks and does not falls under the scope of the WMO, no monitoring is needed.

8. ETHICAL CONSIDERATIONS

8.1 Regulation statement

This study will be conducted according to the principles of the Declaration of Helsinki (WORLD MEDICAL ASSOCIATION DECLARATION OF HELSINKI) Ethical Principles for Medical Research Involving Human Subjects Version Edinburgh, Scotland, October 2000, with Note of Clarification on paragraph 29 added by the WMA General Assembly, Washington 2002 end note of clarification on paragraph 30 added by the WMA General Assembly, Tokyo 2004 and in accordance with the Medical Research Involving Human Subjects Act (WMO) and other guidelines, regulations and Acts.

8.2 Recruitment and consent

Eligible patients will be informed about the study by the supervising physician (e.g. gynaecologist, surgeon or medical oncologist) primarily treating the malignancy. The patient will also obtain written information about the study. The patient can think about participation and discuss the study with her family. They will be given enough time to consider their decision and are free to reconsider their decision at any moment during the trial. In case of participation the informed consent should be signed prior to registration of patient data. This is applicable for the prospective part of this study. An exception is made for the retrospective part of this registration study; retrospective data without the need for follow-up may be collected anonymously without a signed consent form for evaluation of quality of care since it does not fall under the scope of the WMO.

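### Women registered late and then followed must have survived to consent, but the protocol lists no registration date, so survival counted from diagnosis would be overstated

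*Protocol*

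**What the plan says.** Protocol section 3.4 states "Patients can be included both prospectively and retrospectively". Neither that section nor the eligibility criteria in 3.2 and 4.2 limit the interval from diagnosis or treatment to registration.

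The items that section 3.4 lists as baseline include outcomes. The oncological items run through "the date of diagnosis, tumour histology, stage of the disease, the type of treatment, cancer recurrence and survival". The fertility items include "menstrual pattern after cancer treatment, conception (artificial or natural), obstetrical complications", followed by details of delivery, and the paediatric items cover the newborn. The date of diagnosis is the only date in the baseline list. The annual update adds dates of relapse and death. No date of consent or registration appears among the collected data.

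Section 8.2 requires that "In case of participation the informed consent should be signed prior to registration of patient data", and its next sentence confines this to the prospective part. The exception is narrow: "retrospective data without the need for follow-up may be collected anonymously without a signed consent form".

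Section 3.1 makes the oncological outcome, compared with a control group, the primary objective. Section 6 names no time-to-event method and no time origin.

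**The concern.** Read together, sections 3.4 and 8.2 create a group of women who are found some time after diagnosis and are to be followed from then on. They fall outside the consent waiver, so they must be alive to sign. Those who died between diagnosis and the time they would have been approached cannot join this group.

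This is left truncation. If such women are treated as at risk from the date of diagnosis, the interval up to consent is time in which they could not have died, yet it counts as observed survival. Choosing patients without regard to outcome does not cure this, because the condition of being alive at consent remains.

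The standard remedy is delayed entry, which needs a date of entry for each woman. The data listed in section 3.4 do not include one. At stake are the absolute survival figures meant to inform patients and clinicians and, if entry lag differs between cases and controls, the primary comparison.

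**Working it through.** **Inputs.** The protocol gives no lag distribution, length of follow-up or expected survival by tumour type. Its only survival anchor is the figure of more than 70% for cancers at ages 20 to 49 (sections 1 and 2), which is not stated as a 5-year figure. True 5-year survival of 70%, 80% and 90%, a constant hazard, and all entry lags below are therefore assumptions. The target of 500 cases and 500 controls per tumour type (section 3.3) and two-sided P < .05 (section 6) come from the protocol. The 500 cannot be reproduced, because no power, effect size or event rate is stated.

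**Step 1: everyone enters at one fixed time.** With true 5-year survival of 70%, the hazard is −ln(0.70)/5 = 0.0713 per year. Given that a woman is alive at entry time a, apparent 5-year survival from diagnosis is exp(−0.0713 × (5 − a)):

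- a = 0.25 years: exp(−0.0713 × 4.75) = 71.3%
- a = 1 year: exp(−0.0713 × 4) = 75.2%
- a = 2 years: exp(−0.0713 × 3) = 80.7%
- a = 3 years: exp(−0.0713 × 2) = 86.7%

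**Step 2: entry spread over time.** One million women were simulated per scenario, with exponential survival, entry lag uniform from 0 to L years, entry only if alive, and 5 years of follow-up after entry. The table shows Kaplan-Meier 5-year survival with every woman counted as at risk from diagnosis.

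| True survival | All late, L = 2 | All late, L = 5 | All late, L = 10 | Half late, L = 5 |
|---|---|---|---|---|
| 0.70 | 0.752 | 0.833 | 0.901 | 0.760 |
| 0.80 | 0.836 | 0.893 | 0.941 | 0.843 |
| 0.90 | 0.919 | 0.948 | 0.973 | 0.924 |

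When the risk set started at entry, the estimate was within 0.002 of the truth in every scenario.

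**Step 3: effect on a comparison.** If both groups have the same lags and true survival, both estimates rise alike. If only one group enters late and true survival is equal, the spurious difference is the table entry minus the truth. For L = 5 it is 0.131, 0.092 and 0.048 at true survival of 0.70, 0.80 and 0.90. A two-proportion test with 500 per group would then reach P < .05 with probability of about 1.00, 0.98 and 0.82. For L = 2 the differences are 0.051, 0.036 and 0.019, and the probabilities 0.44, 0.31 and 0.18. For scale, 500 per group has 80% power for drops of 0.084, 0.076 and 0.060 from those survival levels.

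**Step 4: pregnancy.** At an assumed 0.06 pregnancies per year, with death as a competing event, the true 5-year proportions are 0.220, 0.234 and 0.247 at true survival of 0.70, 0.80 and 0.90. With all women late and L = 5 they read 0.245, 0.251 and 0.256. Across L = 2 to 10 with all women late, the overstatement is about 0.3 to 3 points.

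**The case against.** The strongest reply is that the protocol fixes no analysis that would be biased. It never says that survival will be counted from diagnosis with everyone at risk from day 0, and the definition of risk sets can be left to an analysis plan that is not at hand. Section 3.4 describes its items as the most important ones, so the list need not be complete, and a consent date may be recoverable at the sites. Part of this stands: the bias is conditional on the analysis. But an analysis plan cannot apply delayed entry from the data as listed. That a date might be recovered from consent forms across international sites is a reason to collect it now.

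Four stronger readings are tempting, and the documents do not support them:

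- *That consent conditions every woman on survival.* Section 8.2 confines the consent sentence to the prospective part, and women who died can enter through the anonymous retrospective route. The point is limited to women registered late who are also to be followed. The protocol does not describe that group; it follows from how narrow the waiver is.
- *That cases enter later than controls, so the bias favours fertility sparing.* A reader might infer this from the mention of obstetricians: "newsletters, presentation at conferences for obstetricians, oncologists, haematologists". But that is one recruitment list, with no separate route for controls, and section 8.2 has the physician treating the malignancy inform patients.
- *That the baseline list shows late entry to be planned.* It may equally be the whole data set under a poor heading. The list accommodates late entry; it does not show how common it will be.
- *That pregnancy is materially inflated.* Through survivorship alone the effect is small. Selection of women because they conceived would be a further problem, but the protocol neither states it nor allows it to be sized.

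**Conclusion.** The point holds for consented, followed women who are registered late. If their survival is counted from diagnosis without delayed entry, absolute survival is overstated, and the listed data do not allow that to be corrected.

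The size depends on lags that the protocol does not give. With all women entering late, the simulated overstatement at 5 years is about 2 to 13 points for lags up to 2 or 5 years, and about 7 to 20 points for lags up to 10 years. It is smaller when only some women enter late and when true survival is higher. Women entering by the anonymous route dilute it, because they are not conditioned on being alive.

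The comparison of cases with controls is biased if entry lag, or the mix of consented and anonymous routes, differs between the groups. Its direction cannot be told from the protocol. In the one-sided scenarios the artefact can be as large as the differences that 500 per group could detect. With equal lags, equal route mix and equal true survival, the between-group bias disappears, but the absolute figures stay inflated.

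**What to change.** In section 3.4:

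1. Add the date of consent or registration to the collected data, and the entry route: consented with follow-up, or anonymous retrospective.
2. State that consented women enter the risk set for the oncological comparison at their registration date (delayed entry), with time still measured from diagnosis.
3. State that relapses and pregnancies before registration are recorded as history and not counted in the prospective rates.
4. Report the anonymous retrospective women separately.

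The cost is two items on the case report form and a short rule. The real downside is less counted person-time and fewer counted events from late-registered women, which matters against a target of 500 per tumour type. If late registration turns out to be common, that loss will not be trivial. Delayed entry also assumes that the time of entry is unrelated to prognosis. It removes the guaranteed survival time but not any selection of women because of their outcome.
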